8.1.1 Dose Discontinuation in Nivolumab and Ipilimumab Combination

Any event that leads to delay in dosing lasting > 6 weeks for nivolumab or > 12 weeks for ipilimumab from the previous dose requires discontinuation, with the following exceptions:

- Dosing delays to allow for prolonged steroid tapers to manage drug-related adverse events are allowed.
- Dosing delays from the previous dose that occur for non-drug-related reasons may be allowed if approved by the BMS Medical Monitor (or designee).

Prior to re-initiating treatment in a participant with a dosing delay lasting > 6 weeks for nivolumab or >12 weeks for ipilimumab, the BMS Medical Monitor (or designee) must be consulted. Tumor assessments should continue as per protocol even if dosing is delayed. Periodic study visits to assess safety and laboratory studies should also continue every 6 weeks or more frequently if clinically indicated during such dosing delays.

Any adverse event, laboratory abnormality, or intercurrent illness which, in the judgment of the Investigator, presents a substantial clinical risk to the participant with continued nivolumab dosing.

The assessment for discontinuation of nivolumab should be made separately from the assessment made for discontinuation of ipilimumab. Although there is overlap among the discontinuation criteria, if discontinuation criteria are met for ipilimumab but not for nivolumab, treatment with nivolumab may continue if ipilimumab is discontinued.

If a participant in the nivolumab/ipilimumab combination arm meets criteria for discontinuation and the investigator is unable to determine whether the event is related to both or one study drug, the participant should discontinue both nivolumab and ipilimumab and be taken off the treatment phase of the study.

8.1.2 Dose Discontinuation in Nivolumab Monotherapy Arm

Any event that leads to delay in dosing lasting > 10 weeks from the previous dose requires discontinuation, with the following exceptions:

- Dosing delays to allow for prolonged steroid tapers to manage drug-related adverse events are allowed.
- Dosing delays that occur for non-drug-related reasons may be allowed if approved by the BMS Medical Monitor (or designee).

Prior to re-initiating treatment in a participant with a dosing delay lasting > 10 weeks, the BMS Medical Monitor (or designee) must be consulted. Tumor assessments should continue as per protocol even if dosing is delayed. Periodic study visits to assess safety and laboratory studies should also continue every 6 weeks or more frequently if clinically indicated during such dosing delays.

8.1.3 Post Study Treatment Study Follow-up

In this study, overall survival is a key endpoint of the study. Post treatment follow-up is of critical importance and is essential to preserving participant safety and the integrity of the study. Participants who discontinue study treatment must continue to be followed for collection of outcome and/or survival follow-up data as required and in line with [Section 5](#) until death or the conclusion of the study.

BMS may request that survival data be collected on all treated/randomized participants outside of the protocol defined window (See [Table 2-5](#) in Schedule of Activities). At the time of this request, each participant will be contacted to determine their survival status unless the participant has withdrawn consent for all contacts or is lost to follow-up.

8.2 Discontinuation from the Study

Participants who request to discontinue study treatment will remain in the study and must continue to be followed for protocol specified follow-up procedures. The only exception to this is when a participant specifically withdraws consent for any further contact with him/her or persons previously authorized by participant to provide this information.

- Participants should notify the investigator of the decision to withdraw consent from future follow-up **in writing**, whenever possible.
- The withdrawal of consent should be explained in detail in the medical records by the investigator, as to whether the withdrawal is from further treatment with study treatment only or also from study procedures and/or post treatment study follow-up, and entered on the appropriate CRF page.
- In the event that vital status (whether the participant is alive or dead) is being measured, publicly available information should be used to determine vital status only as appropriately directed in accordance with local law.
- If the participant withdraws consent for disclosure of future information, the sponsor may retain and continue to use any data collected before such a withdrawal of consent.

8.3 Lost to Follow-Up

- All reasonable efforts must be made to locate participants to determine and report their ongoing status. This includes follow-up with persons authorized by the participant.
- Lost to follow-up is defined by the inability to reach the participant after a minimum of **three** documented phone calls, faxes, or emails as well as lack of response by participant to one registered mail letter. All attempts should be documented in the participant's medical records.
- If it is determined that the participant has died, the site will use permissible local methods to obtain date and cause of death.
- If investigator's use of third-party representative to assist in the follow-up portion of the study has been included in the participant's informed consent, then the investigator may use a Sponsor retained third-party representative to assist site staff with obtaining participant's contact information or other public vital status data necessary to complete the follow-up portion of the study.
- The site staff and representative will consult publicly available sources, such as public health registries and databases, in order to obtain updated contact information.
- If after all attempts, the participant remains lost to follow-up, then the last known alive date as determined by the investigator should be reported and documented in the participant's medical records.

9 STUDY ASSESSMENTS AND PROCEDURES

- Study procedures and timing are summarized in the Schedule of Activities.
- Protocol waivers or exemptions are not allowed.
- All immediate safety concerns must be discussed with the Sponsor immediately upon occurrence or awareness to determine if the participant should continue or discontinue treatment.
- Adherence to the study design requirements, including those specified in the Schedule of Activities, is essential and required for study conduct.
- All screening evaluations must be completed and reviewed to confirm that potential participants meet all eligibility criteria before randomization. The investigator will maintain a

screening log to record details of all participants screened and to confirm eligibility or record reasons for screening failure, as applicable.

- Procedures conducted as part of the participant's routine clinical management (eg, blood count) and obtained before signing of informed consent may be utilized for screening or baseline purposes provided the procedure meets the protocol-defined criteria and has been performed within the timeframe defined in the Schedule of Activities.

Additional measures, including non-study required laboratory tests, should be performed as clinically indicated or to comply with local regulations. Laboratory toxicities (e.g. suspected drug induced liver enzyme evaluations) will be monitored during the follow-up phase via on-site/local labs until all study drug-related toxicities resolve, return to baseline, or are deemed irreversible.

Evaluate participant immediately to rule out cardiac or pulmonary toxicity if participant shows cardiac- or pulmonary-related signs (hypoxia, abnormal heart rate, or changes from baseline) or symptoms (eg, dyspnea, cough, chest pain, fatigue, palpitations).

Some of the assessments referred to in this section may not be captured as data in the eCRF. They are intended to be used as safety monitoring by the treating physician. Additional testing or assessments may be performed as clinically necessary or where required by institutional or local regulations.

9.1 Efficacy Assessments

Efficacy will be based on imaging assessments. For solid tumors, response will be assessed using RECIST 1.1 for solid tumors (see [appendix 7](#)). For CNS tumors, response will be assessed using RANO 2010 criteria⁵³ supplemented by clinical neurologic examination and performance status, as well as additional considerations as applicable e.g. adverse events or steroid requirement. (See [Appendix 8](#)).

9.1.1 Imaging Assessment for the Study

Images will be submitted to an imaging core lab and may undergo blinded independent central review (BICR) at any time during the study. Prior to scanning the first participant sites should be qualified as well as understand the image acquisition guidelines and submission process as outlined in the CA209848 Imaging Manual provided by the imaging core lab. For CNS participants, sites need to follow qualification procedures within the imaging manual to demonstrate the ability to perform required MRI sequences for this study.

Screening and on study tumor assessment will take place in accordance with the [Section 2](#) Schedule of Activities, according to appropriate response criteria ([Appendix 7](#) and [Appendix 8](#)).

Any additional imaging that may demonstrate tumor response or progression (including scans performed at unscheduled timepoints and/or at an outside institution) should be collected for RECIST 1.1 tumor assessment and submitted to the BICR.

Scans should be performed until BICR confirmation of progression or treatment discontinuation (including treatment beyond progression), whichever occurs later.

9.1.2 Methods of Measurement

9.1.2.1 Solid tumors

Contrast-enhanced CT of the chest, abdomen, pelvis, and all other known and/or suspected sites of disease should be performed for tumor assessments. Images should be acquired with slice thickness of 5 mm or less with no intervening gap (contiguous). Every attempt should be made to image each participant using an identical acquisition protocol on the same scanner for all imaging timepoints. Tumor measurements should be made by the same investigator or radiologist for each assessment whenever possible. Change in tumor measurements and tumor response to guide ongoing study treatment decisions will be assessed by the Investigator using the RECIST 1.1 criteria.

Should a participant have contraindication for CT intravenous contrast, a non-contrast CT of the chest and a contrast-enhanced MRI of the, abdomen, pelvis, and other known/suspected sites of disease should be obtained.

Should a participant have contraindication for both MRI and CT intravenous contrasts, a non-contrast CT of the chest and a non-contrast MRI of the abdomen, pelvis, and other known/suspected sites of disease should be obtained.

Should a participant have contraindication for MRI (e.g., incompatible pacemaker) in addition to contraindication to CT intravenous contrast, a non-contrast CT of the chest, abdomen, pelvis, and other known/suspected sites of disease is acceptable.

Use of CT component of a PET-CT scanner: Combined modality scanning such as with PET-CT is increasingly used in clinical care, and is a modality/technology that is in rapid evolution; therefore, the recommendations outlined here may change rather quickly with time. At present, low dose or attenuation correction CT portions of a combined PET-CT are of limited use in anatomically-based efficacy assessments and it is therefore suggested that they should not be substituted for dedicated diagnostic contrast-enhanced CT scans for anatomically-based RECIST 1.1 measurements. However, if a site can document that the CT performed as part of a PET-CT is of identical diagnostic quality to a diagnostic CT (with IV and oral contrast), then the CT portion of the PET-CT can be used for RECIST 1.1 measurements. Note, however, that the PET portion of the CT introduces additional data that may bias an investigator if it is not routinely or serially performed.

Bone scan or PET scan is not adequate for assessment of RECIST 1.1 response in target lesions. In selected circumstances where such modalities are the sole modality used to assess certain non-target organs, those non-target organs may be evaluated less frequently. For example, bone scans may need to be repeated only when complete response is identified in target disease or when progression in bone is suspected.

Bone scans may be collected per local standards, as clinically indicated.

MRI of brain should be acquired as outlined in [Section 2](#) (Schedule of Activities). CT of the Brain (without and with contrast) can be performed if MRI is contraindicated.

9.1.2.2 Primary CNS Neoplasms

Brain MRI without and with gadolinium contrast should be performed as outlined in Section 2 (Schedule of Activities). Participants who are unable (due to existent medical condition, ie, pacemaker or ICD device) or unwilling to have a contrast enhanced MRI of the brain at baseline are excluded from the study. Participants who become unable to undergo MRI imaging after the start of participation in the study may continue in the study for assessment of overall survival as long as there is no safety issue which would require monitoring by MRI.

9.1.3 Imaging and Clinical Assessment

Tumor assessments should continue even if dosing is delayed or discontinued. Changes in tumor measurements and tumor responses will be assessed by the same investigator. Investigators will report the number and size of new lesions that appear while on study. Assessments of PR and CR must be confirmed at least 4 weeks (28 days) after initial response. A Best Overall Response of SD requires a minimum of 77 days on study from date of first dose to the date of the first imaging assessment.

For participants with CNS malignancy, RANO 2010 criteria will be used.

Table 9.1.3-1: RANO Criteria for Time-point Response Assessment Incorporating MRI and Clinical Factors

Response	Criteria
CR	Requires all of the following: complete disappearance of all enhancing measurable and nonmeasurable disease; no new lesions; stable or improved nonenhancing (T2/FLAIR) lesions; participants must be off corticosteroids (or on physiologic replacement doses only); and stable or improved clinically. Note: Participants with nonmeasurable disease only cannot have a complete response; the best response possible is stable disease.
PR	Requires all of the following: $\geq 50\%$ decrease compared with baseline in the sum of products of perpendicular diameters (SPD) of all measurable enhancing lesions; no progression of nonmeasurable disease; no new lesions; stable or improved nonenhancing (T2/FLAIR) lesions on same or lower dose of corticosteroids compared with baseline scan; the corticosteroid dose at the time of the scan evaluation should be no greater than the dose at time of baseline scan; and stable or improved clinically. Note: Participants with nonmeasurable disease only cannot have a partial response; the best response possible is stable disease.
SD	Requires all of the following: does not qualify for complete response, partial response, or progression; stable nonenhancing (T2/FLAIR) lesions on same or lower dose of corticosteroids compared with baseline scan. In the event that the corticosteroid dose was increased for new symptoms and signs without confirmation of disease progression on neuroimaging, and subsequent follow-up imaging shows that this increase in corticosteroids was required because of disease progression, the last scan considered to show stable disease will be the scan obtained when the corticosteroid dose was equivalent to the baseline dose.

Table 9.1.3-1: RANO Criteria for Time-point Response Assessment Incorporating MRI and Clinical Factors

Response	Criteria
PD	Defined by any of the following: $\geq 25\%$ increase in sum of the products of perpendicular diameters of enhancing lesions compared with the smallest tumor measurement obtained either at baseline (if no decrease) or best response, on stable or increasing doses of corticosteroids (Stable doses of corticosteroids include participants not on corticosteroids); significant increase in T2/FLAIR nonenhancing lesions on stable or increasing doses of corticosteroids compared with baseline scan or best response after initiation of therapy not caused by comorbid events (eg, radiation therapy, demyelination, ischemic injury, infection, seizures, postoperative changes, or other treatment effects); any new lesion; clear clinical deterioration not attributable to other causes apart from the tumor (eg, seizures, medication adverse effects, complications of therapy, cerebrovascular events, infection, and so on) or changes in corticosteroid dose; failure to return for evaluation as a result of death or deteriorating condition; or clear progression of nonmeasurable disease.

Table 9.1.3-2: Assessment of Best Overall Response

Best Overall Response	Criteria ⁵⁴
CR	CR observed in assessments ≥ 4 weeks apart per RANO
PR	PR observed in assessments ≥ 4 weeks apart per RANO
SD	SD observed and does not qualify for CR or PR or Suspected PD followed with histologic results not confirming PD, and no CR, PR or SD observed
Note: To qualify for SD there must be a minimum on-treatment period of 6 weeks.)	
Not Evaluable (NE)	Insufficient data to determine disease progression or response
PD	No CR, PR, or SD prior to PD

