Table 2-2: On Study Assessments Treatment Phase - Arm A - Nivolumab in Combination with Ipilimumab (CA209848)

Procedure	Day 1	Every 2 weeks (i.e., every subsequent cycle Day 1) (± 3 Days)	Every 6 weeks (i.e. every 3 cycles Day 1 (± 3 Days))	Every 12 weeks (i.e. every 6 cycles Day 1) (± 7 Days)	Notes For the purposes of this table, a cycle refers to nivolumab every 2 weeks
Vital signs	X	X			Temperature, blood pressure, and heart rate. Must be performed prior to dosing.
Concomitant medication	Continuously				
Adverse events (including serious and non-serious) assessment	Continuously				Record at each visit. All AEs (SAEs or non-serious AEs), including those associated with SARS-CoV-2 infection, must be collected continuously throughout the treatment period. Adverse events and laboratory values will be graded according to the NCI-CTCAE version 5.
Laboratory Assessments					
Hematology and chemistry	X	X			See Section 9.4.3 Clinical Safety Laboratory Assessments. Must be performed within 72h prior to dosing.
Thyroid function testing	X		X (see note)		Thyroid function testing should be done every 4 weeks (i.e., Day 1 of every other cycle) for the first 10 cycles, and then every 8 weeks until completion of study treatment. Must be performed within 72h prior to dosing.
Pharmacokinetic Assessment	See Section 9.5				
Immunogenicity Assessment	See Section 9.5				
Biomarker assessment	See Section 9.8				
Collection of tumor tissue for biomarkers upon disease progression	See Section 9.8				If a biopsy has been performed and tissue is available, participants are requested to submit fresh tumor tissue for biomarker

Table 2-2: On Study Assessments Treatment Phase - Arm A - Nivolumab in Combination with Ipilimumab (CA209848)

Procedure	Day 1	Every 2 weeks (i.e., every subsequent cycle Day 1) (± 3 Days)	Every 6 weeks (i.e. every 3 cycles Day 1 (± 3 Days)	Every 12 weeks (i.e. every 6 cycles Day 1) (± 7 Days)	Notes For the purposes of this table, a cycle refers to nivolumab every 2 weeks
					research. Tissue submission is optional and biopsy is not required by protocol.
Additional research collection	See Section 9.8.1				
Efficacy Assessments					
Body Imaging				X (see note)	For Solid Tumors: Tumor Assessments should occur every 12 weeks (± 7 days) until BICR confirmation of disease progression or treatment discontinuation(including treatment beyond progression), whichever comes later. See Section 9.1.1 for further details.

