Brain Imaging				X (see note)	For Primary CNS neoplasms: MRI without and with contrast; should have MRI of the brain approximately every 12 weeks (± 7 days) until BICR confirmation of disease progression or treatment discontinuation(including treatment beyond progression), whichever comes later. For Solid Tumors: Participants with a history of brain metastasis or symptoms should have a surveillance brain MRI per standard of care (approximately 12 weeks) or sooner if clinically indicated. See Section 9.1.1 for further details.

Table 2-2: On Study Assessments Treatment Phase - Arm A - Nivolumab in Combination with Ipilimumab (CA209848)

Procedure	Day 1	Every 2 weeks (i.e., every subsequent cycle Day 1) (± 3 Days)	Every 6 weeks (i.e. every 3 cycles Day 1 (± 3 Days))	Every 12 weeks (i.e. every 6 cycles Day 1) (± 7 Days)	Notes For the purposes of this table, a cycle refers to nivolumab every 2 weeks
Other: Bone Scan				X (see note)	As clinically indicated per local standards. See Section 9.1.1 for further details.
Outcomes Research					
EORTC QLQ-C30 and EQ-5D questionnaires	X		X		Each assessment should be completed at the start of the clinic visit prior to dosing or any study-related procedures. Only applies to participants ≥ 18 years of age at baseline. If the dose is delayed, then PRO completion should also be delayed and synchronized with the delayed dosing. See Section 9.10 for more details.
Study Treatment					
Contact IRT	X	X			Within 3 days prior to dosing for study drug vial assignment
Nivolumab 240 mg Q2W (adults and adolescents ≥ 40kg)	X	X			Participants should be dosed within 3 days from the scheduled dose. Participants may be dosed no less than 12 days from the previous dose.
Nivolumab 3 mg/kg Q2W (adolescents < 40 kg)	X	X			Participants should be dosed within 3 days from the scheduled dose. Participants may be dosed no less than 12 days from the previous dose.
Ipilimumab 1 mg/kg Q6W (all participants)	X		X (see note)		Ipilimumab should be administered every 6 weeks (i.e., every 3 cycles, Day 1). Participants should be dosed within 3 days from the scheduled dose

Note: Mention of adolescents is not applicable for sites in Belgium or the Netherlands as adolescent participants will not be included in these countries.

Table 2-3: On Study Assessments Treatment Phase - Arm B - Nivolumab Monotherapy (CA209848)

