
The investigator-assessed ORR
	
Investigator-assessed ORR will be summarized by binomial response rates and their corresponding two-sided 95% exact CIs using Clopper-Pearson method.

The investigator-assessed DOR
	
Investigator- assessed duration of response (DOR) will be estimated for all randomized participants who achieve confirmed PR or CR using the Kaplan-Meier (KM) product-limit method. Median values of DOR, along with two-sided 95% CI using Brookmeyer and Crowley method, will also be calculated. Probability of achieving $DOR \geq 6$ months will be calculated using KM method with 95% CI.

TTR is defined as the time from randomization date to the date of the first confirmed response, as assessed by the BICR.
	
Time to response (TTR) will be summarized using descriptive summary statistics for the responders.

Endpoint Definition	Statistical Analysis Methods

CBR is defined as the number of participants with a best overall response (BOR) of confirmed complete response (CR) or partial response (PR) or stable disease (SD) divided by the number of randomized participants.
	
BICR and Investigator assessed CBR will be summarized by binomial response rates and their corresponding two-sided 95% exact CIs using Clopper-Pearson method.

OS is defined as the time from the randomization date to the date of death.
	
Time to event distribution will be estimated using Kaplan Meier techniques. Median OS along with 95% CI will be constructed based on a log-log transformed CI for the survivor function. Rates at some fixed timepoints (6, 12, 18 and 24 months) will be derived from the Kaplan Meier estimate and corresponding confidence interval will be derived based on Greenwood formula for variance derivation and on log-log transformation applied on the survivor function.
 
Participants without documentation of death will be censored on the last date the participant was known to be alive.

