2.3.3 Best Overall Response

Best response determination of complete or partial response requires confirmation: Complete or partial responses may be claimed only if the criteria for each are met at a subsequent time point of ≥ 4 weeks (28 days) later. In this circumstance, the best overall response can be interpreted as in Table 2.3.3-1. When SD is believed to be best response, it must meet the protocol specified minimum time from the date of first treatment or randomization date.

For example, if the first scheduled follow-up imaging visit is Week 6 (± 7 days) for a particular protocol, a Best Response of SD can only be made after the subject is on-study for a minimum of 6 weeks (42 days) minus 7 days, for an absolute minimum time on-study of 35 days from the reference start date (reference date is considered Day 1 on study). If the subject is not on-study for at least this amount of time, any tumor assessment indicating stable disease before this time period will have a Best Response of NE unless PD is identified.

Special note on response assessment: When nodal disease is included in the sum of target lesions and the nodes decrease to ‘normal’ size (< 10 mm), they may still have a measurement reported on scans. This measurement should be recorded even though the nodes are normal in order not to overstate progression should it be based on increase in size of the nodes. As noted earlier, this means that patients with CR may not have a total sum of ‘zero’ on the case report form (CRF).

Table 2.3.3-1: Best Overall Response (Confirmation of CR and PR Required)		
Overall Response First Time Point	Overall Response Subsequent Time Point	Best Overall Response
CR	CR	CR
CR	PR	SD, PD OR PR ^a
CR	SD	SD provided minimum criteria for SD duration met, otherwise, PD
CR	PD	SD provided minimum criteria for SD duration met, otherwise, PD

Table 2.3.3-1: Best Overall Response (Confirmation of CR and PR Required)		
Overall Response First Time Point	Overall Response Subsequent Time Point	Best Overall Response
CR	NE	SD provided minimum criteria for SD duration met, otherwise, NE
PR	CR	PR
PR	PR	PR
PR	SD	SD
PR	PD	SD provided minimum criteria for SD duration met, otherwise, PD
PR	NE	SD provided minimum criteria for SD duration met, otherwise, NE
NE	NE	NE

CR = complete response, PR = partial response, SD = stable disease, PD = progressive disease, and NE = inevaluable

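### The minimum time for stable disease in Section 9.1.3 runs to the first scan and conflicts with Appendix 7 and the RANO table, so the same scans can give different clinical benefit rates

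*Combined protocol and SAP*

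**What the plan says.** Section 9.1.3 sets the condition for calling SD the best response: this classification "requires a minimum of 77 days on study from date of first dose to the date of the first imaging assessment". The sentence is not limited to RECIST 1.1 or to scheduled scans.

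The same section then says "For participants with CNS malignancy, RANO 2010 criteria will be used". Table 9.1.3-2, which defines best overall response under RANO, carries its own note: "To qualify for SD there must be a minimum on-treatment period of 6 weeks". That table gives PD only when no CR, PR or SD came earlier.

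Appendix 7, Section 2.3.3 (RECIST 1.1), leaves the length of the minimum to the protocol and lets it start at either first treatment or randomization. It frames the test as time on study. For a participant who has not been on study that long, "any tumor assessment indicating stable disease before this time period will have a Best Response of NE unless PD is identified".

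On imaging, Section 2 says for solid tumours: "Tumor Assessments should occur every 12 weeks (± 7 days) until BICR confirmation of disease progression". Primary CNS tumours have brain MRI at the same interval with the same window. Section 9.1.1 asks for additional imaging to be collected and sent to BICR, "including scans performed at unscheduled timepoints and/or at an outside institution".

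Section 10.3.1 says "CBR is defined as the number of participants with a best overall response (BOR) of confirmed complete response", and goes on to count PR and SD as well, over randomized participants. It sets no minimum duration for SD. CBR is a secondary endpoint by BICR and by investigator, in both TMB populations and both arms.

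**The concern.** Three passages decide whether a participant has SD, and they ask different questions. Section 9.1.3 asks when the first scan took place. Appendix 7 asks how long the participant has been on study. Table 9.1.3-2 asks how long the participant was on treatment. When the first scan is on schedule the answers usually agree. When there is an earlier scan they need not.

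Under the literal Section 9.1.3 rule, someone who stays stable for months drops out of the CBR numerator because of one extra early scan. Under the RANO table, an early scan can do the reverse and turn a best response of PD into SD. Extra scans are plausibly prompted by symptoms or toxicity, so they would not fall at random.

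The same minimum also decides other cases. In Appendix 7, Table 2.3.3-1, an unconfirmed CR or PR followed by PD or a non-evaluable scan becomes SD only if the SD minimum is met.

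**Working it through.** **1. Reproduce the 77 days.** Appendix 7 gives a worked example: first scheduled scan minus its window, 42 − 7 = 35 days. With this trial's schedule, 12 × 7 − 7 = 77 days, which matches Section 9.1.3. The first scheduled scan falls between day 84 − 7 = 77 and day 84 + 7 = 91.

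The RANO note is 6 × 7 = 42 days, a gap of 77 − 42 = 35 days. No 6-week scan is planned for CNS tumours, so the 42 days do not come from this schedule.

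**2. Apply each rule to the same scans.** Days are counted from first dose, and treatment lasts at least 42 days unless stated. Appendix 7 applies to solid tumours and is used here with 77 days, tested scan by scan. Table 9.1.3-2 applies to primary CNS tumours.

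| Scans | 9.1.3, literal | Appendix 7 | Table 9.1.3-2 |
|---|---|---|---|
| SD day 84 | SD | SD | SD |
| SD day 50, SD day 84 | not SD (50 < 77) | SD | SD |
| SD day 50, PD day 84 | not SD | not SD | SD |
| PD day 84 only | not SD | not SD | not SD |
| Treatment stopped day 30, SD day 84 | SD | SD | not SD (30 < 42) |

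Row 2 is the conflict between Section 9.1.3 and Appendix 7 for solid tumours. Row 3 is the conflict between Section 9.1.3 and the table for CNS tumours (day 50 is about week 7). Rows 3 and 4 together show that, under the table, an early scan alone changes the classification.

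**3. Can early scans occur?** Yes. Section 9.1.1 provides for unscheduled scans. Section 7.7.3 asks for an evaluation for progression before palliative local therapy, particularly if the last assessment was more than 4 weeks earlier. The sentence in Section 9.1.1 names RECIST 1.1 assessment, so for RANO participants the handling of an off-schedule MRI is less explicit.

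**4. Start dates.** Section 9.1.3 counts from first dose. Table 9.1.3-2 counts time on treatment. Appendix 7 allows first treatment or randomization. The best-response window in Section 10.3.1 opens at randomization. Treatment should start within 3 calendar days of randomization (Sections 7.1.1 and 7.1.2), so this difference is small, but it can matter at the edge of the window.

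**5. Size.** Sections 10.1 and 10.3.6 plan 76 combination-arm and 38 monotherapy participants per TMB population. One reclassified participant moves CBR by 1/76 = 1.3 points or 1/38 = 2.6 points.

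**6. Check the repair.** Suppose the rule for all tumours is SD or better on or after day 77 and before progression. Row 2 becomes SD. Row 3 becomes not SD, the same as row 4. An early SD scan then changes neither outcome.

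**The case against.** The best defence is that the passages can be read together. Appendix 7 defers to a protocol minimum, Section 9.1.3 supplies it, and the number is exactly the first scheduled scan minus its window. On that view the first imaging assessment means the first scheduled one, and the participant in row 2 is SD. Likewise, the 6-week note sits in the RANO table and may be a specific rule beside a general one. Pooling RECIST and RANO participants is by design, and a CNS participant whose first scan is on schedule passes both time limits if treatment lasted 6 weeks. Section 10.3 also leaves data handling to an SAP to be finalized before database lock, which could settle the derivation.

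Much of this is plausible as intent. It is not what the text says. Section 9.1.3 does not say scheduled, and Section 9.1.1 brings unscheduled scans in. Appendix 7 cannot override Section 9.1.3 on the minimum, because it defers to the protocol for it. If two minimums were meant, the 77-day sentence would need to be limited to RECIST, and it is not. No passage in the text supplied says which rule governs best response in the CBR analysis.

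One caution stands. Appendix 7 is conditioned on time on study, so reading it as a scan-by-scan test, as in row 3, is an interpretation. Row 2 does not depend on that interpretation.

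**Conclusion.** The point holds. The length of 77 days is sound. What needs correcting is that the interval ends at the first scan, and that the RANO table sets a different, unreconciled minimum for CNS tumours on the same scan schedule. The firm size is 1.3 points of CBR per reclassified participant of 76, or 2.6 of 38.

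Three stronger readings are tempting, and the documents do not support them:

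- **That CBR would shift by several points overall.** This needs the rate of scans before day 77 and the share of those participants with SD as best response. The documents give neither.
- **That the 15% cap gives the number of CNS participants.** A cap is a limit, not an expected share, and Section 5.2 sets it on the total sample. It gives 0.15 × 76 = 11.4 if applied within the 76, but 0.15 × 183 = 27.45 for the whole trial. No CNS count is given, and Section 10.1 plans a pooled analysis of all tumour types.
- **That the primary result is at risk.** ORR requires confirmed CR or PR, so the SD rule does not touch it. Duration of response, which is estimated in confirmed responders, is also unaffected.

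**What to change.** Replace the SD sentence in Section 9.1.3 with:

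> *A best overall response of SD requires at least one assessment of SD or better on or after day 77 from first dose and before progression or subsequent therapy (the Section 10.3.1 best-response window); an earlier SD scan neither qualifies nor disqualifies a participant.*

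Then:

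- Use the same start date in Appendix 7, Section 2.3.3.
- Reconcile the 6-week note in Table 9.1.3-2. Either align it to 77 days, or limit the Section 9.1.3 sentence to RECIST 1.1 and state that the pooled CBR uses two minimums.
- Keep, as a stated exception, the route in Table 9.1.3-2 by which suspected progression not confirmed by histology counts as SD. The sentence above would otherwise remove it.

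The cost is one sentence, one table note, one start date and the best-response derivation code, all fixed before database lock. If the note is aligned to 77 days, a few CNS participants with only an early SD scan may no longer count toward CBR.
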